Determining whether this highly-effective reversible contraceptive method is a safe and viable option for HIV-infected women on HAART will broaden these patients' contraceptive options, particularly when they wish to avoid pregnancy for an extended period of time. The knowledge gained from this study will also help determine whether the lifespan of Nexplanon®/Implanon® is reduced in women taking reduced-dose efavirenz. After Nexplanon®/Implanon® is inserted, there is an initial burst release of etonogestrel, and peak serum concentration is reached at a mean of 4 days after placement[7]. Serum ENG concentrations decline slowly over the three-year lifespan of the implant, and this study will provide information as to whether ENG concentrations remain sufficient to reliably suppress ovulation when EFV is taken simultaneously. If reduced-dose EFV causes ENG concentrations to decrease below the ovulation suppression threshold, the ENG implant may need to be replaced prior to the licensed three years.

10. Payment and Remuneration

- a. Detail compensation for participants including possible total compensation, proposed bonus, and any proposed reductions or penalties for not completing the protocol.

Participants will be compensated as follows:

- Screening visit = \$75
- Enrollment visit = \$45
- Follow-up visits (total of 12) = \$60 each = \$720 total
- Bonus payment for completion of study = \$180
- Parking/Bus tokens (total of 14) = \$5 each = \$70 total

This comes to a total of \$1090 for each participant at the end of the study. The bonus payment at the completion of the study will be made if there have been no significant deviations from the study protocol. Participants will not be compensated for visits that are not completed, and they will not receive the bonus if they are missing data for three or more visits.

11. Costs

- a. Detail costs of study procedure(s) or drug (s) or substance(s) to participants and identify who will pay for them.

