This will be a prospective, single arm pilot pharmacokinetic (PK) study. We will recruit 18 healthy, HIV-negative women aged 18 to 40 years who are using Nexplanon®/Implanon® for contraception and who are willing to take a reduced dose of EFV for 2 weeks. We will limit enrollment to women who have had the ENG implant in place 12 to 24 months to avoid the initial burst release of ENG after implant placement, and to target the time frame of concern based on case studies of contraceptive failures among women on HAART. Performing the study in women without HIV infection will allow us to evaluate any interactions between ENG and EFV without having to contend with the effects of other drugs that make up typical HAART regimens. A two-week course of EFV will be sufficient for EFV to reach steady-state concentration while minimizing exposure in these healthy volunteers. By using the reduced dose of EFV (400 mg daily instead of the standard 600 mg daily dose)

Over 6 weeks from study entry, we will perform twice-weekly (see visit schedule) quantitative assessments of serum ENG as well as serum hormone concentration analysis, pelvic ultrasound for markers of ovulation, and cervical mucus testing, as described below. Given the slow apparent clearance of ENG and based on previous PK studies, we estimate that sparse sampling will be adequate to assess changes in ENG clearance during EFV administration. EFV will be administered for 14 days from the beginning of the study, after collection of baseline samples for ENG concentration determination. All study procedures will take place at the Johns Hopkins Bayview Medical Center's Clinical Research Unit (CRU). All blood tests will be performed locally except for ENG concentrations, which will be performed at Columbia University

Date: January 5th, 2017

Principal Investigator: [name], MPH

Application Number: NA_00087585

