Data collection: After successful screening, women will be asked to take 14 days of EFV in a once-nightly 400 mg regimen. We will collect blood samples for baseline ENG concentration on the day participants begin taking EFV, before the first dose (Day 1, times 0 hour, 1 hour, and 2 hours). The first dose of EFV will be taken in the evening of Day 1, and the next blood sample for ENG concentration will be drawn twelve to twenty hours after the first dose of EFV. (For example, if a participant takes her first dose of EFV at 10 PM on Day 1, she will be asked to return to the CRU between 10 AM and 6 PM on Day 2.) We will then obtain subsequent samples every 3 to 4 days (+/- 1 day) for the remainder of the two week EFV course and for 4 additional weeks (through Week 6 of study participation). This is a total of 14 outpatient visits, including screening. All serum samples will be analyzed for concentrations of ENG, which will be used to derive the ENG area under the concentration-time curve (AUC), the maximum and minimum observed serum drug concentration (C_{max}, C_{min}), and the apparent average serum concentration at steady-state (C_{ss,avg}) using WinNonlin®. EFV concentrations will be determined from plasma samples obtained at 2 timepoints during EFV administration, and measured using a validated LC/MS/MS assay in the Clinical Pharmacology Analytical Laboratory of the Johns Hopkins Hospital.

Table 1: Participant Visit Schedule and Timing of Study Assessments

Visit	Screening	Study Entry			Week 1		Week 2		Week 3		Week 4		Week 5		Week 6	
		1			2	7	11	14	18	21	25	28	32	35	39	42
Serum Tests		0 hr	1 hr	2 hr												
ENG		X	X	X	X	X	X	X	X	X	X	X	X	X	X	X
EFV					X			X								
FSH		X			X	X	X	X	X	X	X	X	X	X	X	X
LH		X			X	X	X	X	X	X	X	X	X	X	X	X
Estradiol		X			X	X	X	X	X	X	X	X	X	X	X	X
Progesterone		X			X	X	X	X	X	X	X	X	X	X	X	X
Safety Labs	X															X
UPT	X															X
HIV	X															X
TVUS	X				X	X	X	X	X	X	X	X	X	X	X	X
CM	X				X	X	X	X	X	X	X	X	X	X	X	X

Date: January 5th, 2017

Principal Investigator: [name], MPH

Application Number: NA_00087585

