- Nervous system symptoms: dizziness, insomnia, impaired concentration, somnolence, abnormal dreaming, euphoria, confusion, agitation, amnesia, hallucinations, stupor, abnormal thinking, depersonalization. Mild symptoms occurred in 33.3% of patients taking EFV compared to 15.6% of patients in control groups; moderate symptoms occurred in 17.4% of patients taking EFV compared to 7.7% of controls; and severe symptoms occurred in 2% of patients taking EFV compared to 1.3% of controls.
- Rash: 26% of patients taking EFV developed a rash compared to 17% of patients in control groups. A grade 4 rash (erythema multiforme, Stevens-Johnson syndrome, toxic epidermal necrolysis, necrosis requiring surgery, exfoliative dermatitis) was seen in 0.1% of patients treated with EFV and no patients in control groups. Rashes usually occur during the first two weeks of treatment, and are mild-to-moderate maculopapular skin eruptions. The rash typically resolves within one month in patients who continue EFV.
- Hepatotoxicity: it is recommended that liver enzymes be evaluated before and during treatment with EFV, as EFV can cause elevated liver enzymes even in patients without underlying hepatic disease.
- Convulsions: Convulsions have been noted in patients treated with EFV, typically in the setting of a known seizure disorder.
- Lipid elevations: EFV can lead to increased concentrations of total cholesterol and triglycerides. Some HIV-uninfected volunteers who received EFV were noted to have 10-20% increases in total cholesterol from baseline.

Date: January 5th, 2017

Principal Investigator: [name], MPH

Application Number: NA_00087585

- **Fat redistribution:** Body fat may redistribute or accumulate in certain regions of the body, including central obesity, dorsocervical fat enlargement (buffalo hump), peripheral wasting, facial wasting, breast enlargement, and “cushingoid appearance.” This phenomenon has been noted among patients taking antiretroviral therapy in general, and while it has not been specifically linked to EFV, it is a potential adverse reaction to this drug.
- c. Justification and safety information if non-FDA approved drugs without an IND will be administered.

Not applicable

7. Study Statistics

- a. Primary outcome variable.

Primary Outcome: Serum concentrations of ENG before and after two weeks of reduced-dose EFV

- b. Secondary outcome variables.

Secondary Outcomes:

- Serum concentrations of EFV at the start and end of the study period

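### The 30% no-interaction rule may be applied to an AUC or average that includes the days before etonogestrel has settled, which understates the effect of continuous efavirenz

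*Combined protocol and SAP*

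**What the plan says.** Section 4a gives two reasons for the two-week course, one kinetic and one about volunteer safety: "A two-week course of EFV will be sufficient for EFV to reach steady-state concentration while minimizing exposure in these healthy volunteers". Its only statement on ENG kinetics opens "Given the slow apparent clearance of ENG" and supports sparse sampling. The plan gives no ENG half-life and no time for enzyme induction to build up.

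Under Data collection in 4a and in Table 1, ENG is sampled before dosing on Day 1, on Days 2, 7, 11 and 14 of the EFV course, and on Days 18 to 42 after it. For Day 2, "the next blood sample for ENG concentration will be drawn twelve to twenty hours after the first dose of EFV". All these samples feed AUC, Cmax, Cmin and "the apparent average serum concentration at steady-state". No window is stated for any of them.

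Section 7a names the primary outcome as "Serum concentrations of ENG before and after two weeks of reduced-dose EFV". The Interpretation paragraph of 7c does not use that contrast. It compares the ENG pharmacokinetic parameters with published values and infers no important interaction if the difference is under 30%. A separate criterion in the same paragraph looks for two or more of 15 women below the ovulation-suppression threshold, given in 7c as 90 pg/mL.

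**The concern.** That EFV reaches steady state does not establish that ENG has. Three processes run in sequence: EFV accumulates, enzyme activity rises, and ENG drifts down to a lower level. An AUC or average that starts on Day 1 includes days with little or no effect, so on EFV it is not a steady-state quantity. If the window runs to Day 42, it also includes four weeks of recovery.

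The error runs one way, towards a smaller apparent interaction. A result under 30% is to be read as support for using the implant in women who take EFV continuously, and they would reach a lower ENG level than such an average shows.

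**Working it through.** **Starting point.** The plan gives no figure for the time ENG needs to settle, so there is none to reproduce. Its claim about EFV is plausible: with an assumed EFV half-life of 2 days, 13 days of dosing gives 1 − 0.5^(13/2) = 0.989 of steady state. The question is how ENG follows.

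**Inputs from the documents.** Evening doses for 14 days from Day 1; ENG samples on the Table 1 days; the 30% margin from 7c. **Assumed, not in the documents:** a true full-induction fall of 40%, constant implant release, and all half-lives.

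**Case A: induction is instantaneous (kindest to the plan).** Clearance rises by 1/0.6 at the first dose. With ENG half-life h, the percentage fall t days after that dose is

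f(t) = 40 × (1 − exp(−k·t)), with k = ln 2 / (0.6·h).

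Take the first dose 0.46 day after the baseline sample and the Day 2 sample 16 hours (0.667 day) after the dose. The Day 7, 11 and 14 samples then fall at t = 5.54, 9.54 and 12.54 days. For h = 3, k = 0.385 and f = 9.1, 35.3, 39.0 and 39.7%. The linear trapezoid over 13 days is

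[(0 + 9.1)/2 × 1.127 + (9.1 + 35.3)/2 × 4.873 + (35.3 + 39.0)/2 × 4 + (39.0 + 39.7)/2 × 3] / 13 = 380/13 = 29.2%.

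| ENG half-life (days) | Day 1–14 AUC fall | Day 14 fall |
|---|---|---|
| 1 | 34.0% | 40.0% |
| 2 | 31.4% | 40.0% |
| 3 | 29.2% | 39.7% |
| 5 | 25.1% | 37.8% |
| 7 | 21.7% | 34.9% |
| 10 | 17.8% | 30.6% |

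The AUC drops below 30% once the ENG half-life exceeds about 2.6 days. Day 14 does so only beyond about 10.4 days.

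**Case B: induction builds up.** EFV level F (relative to its steady-state mean) has a half-life of 2 days, with the first dose half a day after baseline. Enzyme E and ENG C both start at 1:

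dE/dt = kE·(1 + (1/0.6 − 1)·F − E); dC/dt = kC·(1 − E·C).

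At full induction E = 1/0.6, so C = 0.6. Percentage falls by scenario:

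| Enzyme / ENG half-life (days) | Day 2 | Day 7 | Day 11 | Day 14 | Day 18 | AUC 1–14 | AUC 1–42 |
|---|---|---|---|---|---|---|---|
| 1.5 / 1 | 0.7 | 27.5 | 36.7 | 38.8 | 34.0 | 24.0 | 15.5 |
| 1.5 / 2 | 0.4 | 22.4 | 34.6 | 37.9 | 35.6 | 21.5 | 15.9 |
| 3 / 1 | 0.4 | 20.6 | 32.1 | 36.0 | 35.0 | 20.0 | 16.3 |
| 3 / 2 | 0.2 | 16.1 | 29.3 | 34.6 | 35.5 | 17.5 | 16.5 |
| 6 / 1 | 0.2 | 13.3 | 24.4 | 29.6 | 31.7 | 14.6 | 16.8 |
| 6 / 2 | 0.1 | 10.0 | 21.4 | 27.6 | 31.3 | 12.5 | 16.7 |

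Check of the first row: (0.7/2 × 1 + 28.2/2 × 5 + 64.2/2 × 4 + 75.5/2 × 3)/13 = 312.5/13 = 24.0%.

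Both AUCs are under 30% in all six scenarios. Day 14 is over 30% in four of the six. The lowest scheduled sample (Day 14 or 18) shows 31–39% in all six. The modelled Day 14/Day 11 ratio lies between 0.92 and 0.97.

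**The case against.** A reader might infer that ENG is still falling when EFV stops, or that two weeks is too short. The documents do not support this. They give no ENG half-life or induction rate, and the phrase about slow clearance does not fix one. In Case A, with an ENG half-life of 3 days or less, ENG has essentially settled by Day 14. The averaging bias remains even then, because it comes from the days already passed and not from any further fall.

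Nor is EFV steady state the only reason given for the duration. Limiting exposure in healthy volunteers is the other. It is a legitimate reason, but it does not address ENG timing.

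The best defence is that the plan has other protection. The primary outcome is a before/after concentration, which is much less biased. The rule refers to parameters in the plural, and Cmin exceeds 30% in all six Case B scenarios. The 90 pg/mL criterion is separate and does not depend on an average. No Day 1–14 AUC is defined, so that window is one possible reading.

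Much of this stands, and it limits the claim. What remains is that 7c does not say which parameter decides, over which window, or what happens if they disagree. The threshold criterion does not stop a sub-30% average from being read as no interaction. The other natural window, all samples to Day 42, dilutes the effect at least as far below the margin.

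**Conclusion.** The point holds in a limited form. An ENG AUC or Css,avg that starts on Day 1 understates the fall under continuous EFV in every case examined, and 7c allows such a quantity to decide the no-interaction conclusion. With gradual induction over the assumed ranges, a true 40% fall appears as about 12–24% over Days 1–14 and about 15–17% over Days 1–42, against about 28–39% at Day 14.

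A reader might infer that the rule would always pass a true 40% fall. It would not: with instantaneous induction and an ENG half-life of 1–2 days, the Day 1–14 AUC shows 31–34% and exceeds the margin. The direction of the bias follows from averaging over a transition; its size rests wholly on kinetics that the documents do not give. Cmin and the 90 pg/mL criterion are less affected. The change is worth making because the error favours reassurance and the remedy is a matter of wording.

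**What to change.** In 4a and 7c:

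- Apply the 30% rule to each woman's Day 14 ENG concentration relative to her own Day 1 baseline. This aligns the rule with the primary outcome in 7a.
- Report AUC and Css,avg descriptively, with their windows stated. Do not call an average spanning the transition or the washout a steady-state value.
- Report the Day 14/Day 11 geometric mean ratio with its confidence interval. If it indicates a continuing decline, say that the Day 14 reduction may be a lower bound for continuous EFV. This matters because Day 14 itself fell just under 30% in two of the six Case B scenarios.
- Do not make any numerical fall an automatic bar to the conclusion. With no interaction and equal independent noise, Day 14 or Day 18 would lie below Day 11 with probability 1 − 1/3 = 2/3. Day 18 is also off EFV, so it is not a plateau sample.

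The cost is precision: one end-of-course value is noisier than an average. The plan states no standard deviation, so the loss cannot be quantified here. The comparison with historical controls in the sample-size paragraph of 7c would need rewording to match. Dose, duration, visits and samples do not change.

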- Serum hormonal markers of ovulation (P, E₂, LH, FSH)
- Presence of dominant follicle(s) on transvaginal ultrasound during and after EFV dosing
- Change in cervical mucus quality suggesting ovulation during and after EFV dosing

- c. Statistical plan including sample size justification and interim data analysis.

Sample size: We hypothesize that during co-administration of the ENG implant and reduced-dose EFV, we will detect a decrease in serum ENG concentrations, but that overall contraceptive effect will be maintained. We do not anticipate that any subjects will have a drop in ENG concentration below the threshold needed for ovulation suppression (90 pg/mL)[8]. Using a two-sided Wilcoxon test, a sample size of 15 will have 80% power (with an alpha of 0.05) to detect a 20% difference in ENG concentration between women taking EFV and historical controls. We plan to enroll 18 women to account for a potential 20% drop-out rate.

Data Analysis: We will calculate area under the curve (AUC) and maximum and minimum concentrations of each drug (C_{max} and C_{min}), as noted above. For hormone markers (LH, FSH, E₂, P) we will evaluate change over time as well as whether pertinent threshold levels are reached that could indicate that ovulation has occurred. All serum tests will be evaluated through the Johns Hopkins Division of Clinical Pharmacology, with the exception of etonogestrel concentrations as this assay is not widely available. Serum samples will be frozen and shipped to the Irving Institute for Clinical and Translational Research at Columbia University Medical Center in New York City, which will perform the etonogestrel assay.

Interpretation: If the pharmacokinetic parameters for etonogestrel that are seen in this interaction study are consistent with those published in the literature (less than 30% difference), we will conclude that there is no significant interaction between ENG and reduced-dose EFV. This would support the assertion that Nexplanon®/Implanon® is a safe and effective option for HIV-infected women taking reduced-dose EFV who desire long-acting reversible contraception. However, if two or more women out of a sample of 15 breach the threshold concentration needed for ovulation suppression, it will indicate a statistically and clinically significant decrease in ENG concentration and potential for decreased contraceptive efficacy.

Date: January 5th, 2017

Principal Investigator: [name], MPH

Application Number: NA_00087585

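### Observed ENG Cmin and Cmax depend on the sampling schedule, yet the 30% no-interaction rule against published values does not exclude them

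*Combined protocol and SAP*

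**What the plan says.** Section 4a (Data collection) takes the baseline ENG samples before the first EFV dose ("Day 1, times 0 hour, 1 hour, and 2 hours"). After that, "the next blood sample for ENG concentration will be drawn twelve to twenty hours after the first dose of EFV", and sampling continues at intervals of 3 to 4 days to Week 6. Table 1 places the later ENG samples on Days 2, 7, 11, 14, 18, 21, 25, 28, 32, 35, 39 and 42.

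All serum samples are assayed for ENG and used to derive AUC, "the maximum and minimum observed serum drug concentration", and an average steady-state concentration. No time window is attached to any of these. Section 7c (Data Analysis) repeats the intention without a window: "We will calculate area under the curve (AUC) and maximum and minimum concentrations of each drug".

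Section 7c (Interpretation) supplies the decision rule. If the ENG parameters are "consistent with those published in the literature (less than 30% difference"), the study concludes that there is no important interaction. The rule names no governing parameter and leaves none out. Section 7a gives the primary outcome in terms of concentrations: "Serum concentrations of ENG before and after two weeks of reduced-dose EFV".

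**The concern.** With an oral drug, Cmax and Cmin are features of a dosing interval. The implant releases ENG continuously, so here they are only the highest and lowest of whatever samples happen to be drawn. An observed minimum tends to fall, and an observed maximum to rise, as samples are added and spread over more days. A published Cmin or Cmax from a study with fewer samples is therefore not on the same footing.

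Pooling over all samples adds a second problem. The maximum can come from Day 1, before EFV, or from Days 18-42, after EFV has stopped. A fall during EFV then hardly touches it.

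What is at stake is the conclusion in section 7c. Read on Cmin, the sampling schedule alone pushes towards an apparent interaction. Read on Cmax, it pushes the other way and can hide a real one.

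**Working it through.** **1. Sample counts (section 4a, Table 1).**
- Before EFV: 3 samples, all within two hours on Day 1.
- On EFV: Days 2, 7, 11 and 14, so 4 samples.
- After EFV: Days 18, 21, 25, 28, 32, 35, 39 and 42, so 8 samples.
- Total: 3 + 4 + 8 = 15 samples on 13 days.
- Check against the plan's own figure: 1 screening + 1 entry + 12 follow-up = 14 visits, which agrees with "This is a total of 14 outpatient visits, including screening".

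**2. Assumptions, because the documents give no figures.** Within-woman variation between visits is lognormal with CV 10% to 25%, so the log-scale SD is s = √ln(1 + CV²): 0.0998 at 10%, 0.1980 at 20% and 0.2462 at 25%. Visits are independent. The three Day 1 samples share one value, which leaves 13 effective values. The published study drew k = 2, 4 or 6 samples from women with the same average level.

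**3. Expected extremes.** Let E(k) be the expected maximum of k standard normal values: E(2) = 0.564, E(3) = 0.846, E(4) = 1.029, E(6) = 1.267, E(10) = 1.539, E(12) = 1.629, E(13) = 1.668.

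**4. Pooled extremes against a published value, no EFV effect.** The Cmin ratio is exp(−s[E(13) − E(k)]); the Cmax ratio is its reciprocal.

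| CV | k = 6: Cmin / Cmax | k = 4: Cmin / Cmax | k = 2: Cmin / Cmax |
|---|---|---|---|
| 10% | −3.9% / +4.1% | −6.2% / +6.6% | −10.4% / +11.6% |
| 20% | −7.6% / +8.3% | −11.9% / +13.5% | −19.6% / +24.4% |
| 25% | −9.4% / +10.4% | −14.6% / +17.0% | −23.8% / +31.2% |

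Example at CV 25%, k = 2: 0.2462 × (1.668 − 0.564) = 0.272; exp(−0.272) = 0.762 and exp(0.272) = 1.312.

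**5. Pooled Cmax under a real fall.** Suppose ENG falls by 30% to 50% on Days 7, 11 and 14 only. Those three values then almost never supply the maximum, so the maximum of 13 becomes in effect the maximum of 10. The ratio is exp(−s[E(13) − E(10)]) = exp(−s × 0.129): −1.3% at CV 10% and −3.1% at CV 25%. Simulation of both falls agreed, at about −1% to −3%.

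Combining steps 4 and 5, Cmax would still read from 1.041 × 0.987 = 1.03 (CV 10%, k = 6) to 1.312 × 0.969 = 1.27 (CV 25%, k = 2) times the published value. Every case lies inside the 30% margin despite the real fall.

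**6. If Cmin were compared before and after EFV.** The plan does not state this contrast. Lowest of 12 later samples against Day 1, no EFV effect:
- Day 1 samples independent: exp(−s[1.629 − 0.846]) gives −7.5% to −17.5% (CV 10% to 25%).
- Day 1 samples sharing one value: exp(−s × 1.629) gives −15% to −33%.

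In simulated trials of 15 women with no EFV effect, a two-sided Wilcoxon test of lowest-of-12 against lowest-of-3 rejected in 83% to 98% of trials, for same-day correlation 0 to 0.8. With only the 4 on-EFV samples it rejected in 10% to 48%. Day 14 against the Day 1 mean rejected in 4.1% to 5.0%, which is close to nominal.

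**The case against.** The strongest reply is that the plan never compares Cmin or Cmax with baseline. A reader might infer such a contrast from the primary outcome and conclude that Cmin must fall and Cmax must rise after Day 1. The documents do not support that reading. The abstract speaks of comparing concentrations across time points, section 7a frames the primary outcome as concentrations, and the 30% rule looks to the literature. Even under that contrast the shift is an average: the later Cmin is the lower one in 80% to 92% of women, not in all.

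A reader might also infer that sample count can use up most or all of the 30% margin. For Cmin it never reaches 30% in the range shown, and it passes 15% only with k = 2 and a CV of about 15% or more. Cmax passes 30% in one corner only (CV 25%, k = 2). The larger Day 1 percentages belong to a comparison that the rule does not make.

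Two further points are fair. Correlation between visits would shrink the shifts: a lag-1 correlation of 0.6 turns −15% to −33% into about −13% to −29%. AUC and average concentration are also planned, and pooled Cmin would still register a real fall, so a rule requiring every parameter to pass would not be misled by Cmax alone.

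What remains is that the rule does not say which parameter governs, whether all must pass, or over what window each is taken. As written, both extremes count towards the conclusion.

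**Conclusion.** The point holds in a limited form. The sample counts, the definition as observed extremes and the undifferentiated 30% rule are all in the text. With no EFV effect, pooled Cmin would be about 4% to 24% too low, and pooled Cmax about 4% to 31% too high, against a published value from 2 to 6 samples. A 30% to 50% fall confined to Days 7-14 would move pooled Cmax by only about 1% to 3%.

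These sizes rest on an assumed CV of 10% to 25%, independent visits, assumed published sample counts and, for the last figure, an assumed timing of the fall. The directions do not depend on the exact CV, provided that the published values come from fewer samples.

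A comparison of Day 14 with Day 1 concentrations, which is one natural reading of the primary outcome, is not affected. This is worth correcting before analysis, but it does not undermine the data being collected.

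**What to change.** In section 7c, base the 30% decision on one parameter that does not depend on sample count: the within-woman geometric mean ratio of the Day 14 ENG concentration to the mean of the three Day 1 samples. A time-averaged on-EFV concentration over a stated window could replace Day 14. Either matches the primary outcome in section 7a.

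State the time window for every ENG parameter. Report Cmin and Cmax descriptively by period (before, on and after EFV) with the number of samples behind each, outside the 30% rule. Any comparison with published values should likewise be descriptive and give the published sampling schedule.

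The cost is wording only, since every sample needed is already scheduled. Two customary pharmacokinetic parameters become descriptive. The sample-size sentence, which is framed against historical controls, would need to be aligned with the within-woman comparison.
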